### 5.7.1 Main Variables

Eating patterns and dietary information collected using the following questionnaires:

- Semi-quantitative food frequency questionnaire (FFQ) validated in the Spanish population (20). This questionnaire consists of 137 items. They collect the average food intake over the past year. Food consumption frequencies are recorded in nine levels (never or mostly never, 1-3 times/month, 1 time/week, 2-4 times/week, 5-6 times/week, 1 time/day, 2-3 times/day, 4-6 times/day, and more than 6 times/day). Food consumption frequencies will be calculated as the number of meals per day and multiplied by the weight of the portion sizes indicated in the questionnaire. Nutrient intake will be adjusted for energy intake. In addition, participants who have not made any changes to their dietary habits during the past year prior to the study will be asked at the first visit. Nutritional data will be extracted using the Spanish Food Composition Database (BEDCA), developed by the RedBEDCA and the Spanish Agency for Food Safety and Nutrition (21).  
(An English version is attached at the end of this protocol).
- Mediterranean Diet Adherence Index (aMED) to assess the degree of adherence to the Mediterranean Diet. Based on the Mediterranean Diet Scale (22), which includes the intake of vegetables, legumes, fruits, nuts, grains, red and processed meats, fish, the ratio of monounsaturated/saturated fats, and alcohol; the scoring scale ranges from 0 to 9 points.
- Healthy Eating Index (aHEI), based on the American Dietary Guidelines and the Healthy Eating Pyramid (23), which contains 9 items related to healthy food intake, with a maximum score of 87.5.
- Mediterranean Diet Adherence Screener (MEDAS): The MEDAS (Mediterranean Diet Adherence Screener) is a tool used to assess the degree of adherence to the Mediterranean Diet. It consists of 14 questions that explore different aspects of the characteristic dietary pattern of this diet (24). Each question is assigned a value depending on the frequency or quantity of consumption reported. The total score of the MEDAS questionnaire can range from 0 to 14 points, where a higher score indicates greater adherence to the Mediterranean Diet. This questionnaire provides an overview of an individual's dietary pattern and its alignment with the principles of the Mediterranean diet.

Physical Activity Log:

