## 14. Supplementary material

Semi-quantitative food frequency questionnaire (Translated from the Spanish version)

|   | Never or almost never | Month     | Times/week |     |     | Times/day |     |     |    |
|---|-----------------------|-----------|------------|-----|-----|-----------|-----|-----|----|
|   |                       | 1-3 times | Once       | 2-4 | 5/6 | Once      | 2/3 | 4/6 | +6 |
| Section I: Fruits & Fruit Juices (Items 1–12)                  |                       |           |            |     |     |           |     |     |    |
| 1. Orange (1), grapefruit (1) or tangerines (2)                           |                       |           |            |     |     |           |     |     |    |
| 2. Banana (1)   |                       |           |            |     |     |           |     |     |    |
| 3. Apple or pear (1)  |                       |           |            |     |     |           |     |     |    |
| 4. Fresh orange juice (1 glass, 200 mL)                                   |                       |           |            |     |     |           |     |     |    |
| 5. Bottled or canned fruit juice (200 mL)                                 |                       |           |            |     |     |           |     |     |    |
| 6. Cherries, sour cherries, plums (dessert plate)                         |                       |           |            |     |     |           |     |     |    |
| 7. Grapes (1 bunch or 20 berries)   |                       |           |            |     |     |           |     |     |    |
| 8. Strawberries, raspberries, blackberries (dessert plate)                |                       |           |            |     |     |           |     |     |    |
| 9. Dried fruit (apricots, figs, raisins) (30 g)                           |                       |           |            |     |     |           |     |     |    |
| 10. Other fresh fruit (1 piece or 150 g)                                  |                       |           |            |     |     |           |     |     |    |
| 11. Citrus fruits other than orange or tangerine                          |                       |           |            |     |     |           |     |     |    |
| 12. Fruit salads or compotes (1 bowl)                                     |                       |           |            |     |     |           |     |     |    |

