| Section II: Vegetables & Legumes (Items 13–28)                 |                       |           |            |     |     |           |     |     |    |
| 13. Raw leafy greens or salad vegetables (1 plate)                        |                       |           |            |     |     |           |     |     |    |
| 14. Cooked leafy greens (spinach, chard) (1 plate)                        |                       |           |            |     |     |           |     |     |    |
| 15. Raw cruciferous vegetables (broccoli, cauliflower, cabbage) (1 plate) |                       |           |            |     |     |           |     |     |    |
| 16. Cooked cruciferous vegetables (1 plate)                               |                       |           |            |     |     |           |     |     |    |
| 17. Tomatoes (raw or cooked) (1 medium fruit or 1 plate)                  |                       |           |            |     |     |           |     |     |    |
| 18. Bell peppers, cucumber, celery (1 plate)                              |                       |           |            |     |     |           |     |     |    |
| 19. Onion, garlic, leeks (added in cooking) (1 serving)                   |                       |           |            |     |     |           |     |     |    |
| 20. Other cooked vegetables (eggplant, zucchini, carrots) (1 plate)       |                       |           |            |     |     |           |     |     |    |
| 21. Legumes (lentils, chickpeas, beans) (150 g)                           |                       |           |            |     |     |           |     |     |    |
| 22. Peas (150 g)  |                       |           |            |     |     |           |     |     |    |
| 23. Broad beans (150 g)   |                       |           |            |     |     |           |     |     |    |
| 24. Soy products (tofu, edamame) (100 g)                                  |                       |           |            |     |     |           |     |     |    |
| 25. Potatoes (boiled, baked) (1 medium)                                   |                       |           |            |     |     |           |     |     |    |
| 26. French fries or potato chips (1 portion)                              |                       |           |            |     |     |           |     |     |    |

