| 73. Mayonnaise — 1 tablespoon   |  |  |  |  |  |  |  |
| 74. Cream (liquid or whipped) — 1 tablespoon                          |  |  |  |  |  |  |  |
| 75. Other sauces (ketchup, mustard, barbecue) — 1 tablespoon          |  |  |  |  |  |  |  |
| 76. Pesto, aioli or other oil-based sauces — 1 tablespoon             |  |  |  |  |  |  |  |
| 77. Lard or animal fat — 1 tablespoon                                 |  |  |  |  |  |  |  |
| Section VIII: Beverages (Items 78–94)                          |  |  |  |  |  |  |  |
| 78. Coffee — 1 cup  |  |  |  |  |  |  |  |
| 79. Decaffeinated coffee — 1 cup                                      |  |  |  |  |  |  |  |
| 80. Tea (green, black, etc.) — 1 cup                                  |  |  |  |  |  |  |  |
| 81. Herbal teas (chamomile, mint, etc.) — 1 cup                       |  |  |  |  |  |  |  |
| 82. Milkshakes or flavored milk drinks — 1 glass (200 mL)             |  |  |  |  |  |  |  |
| 83. Soft drinks with sugar — 1 can (330 mL)                           |  |  |  |  |  |  |  |
| 84. Soft drinks without sugar (diet/light) — 1 can (330 mL)           |  |  |  |  |  |  |  |
| 85. Bottled fruit juice (not freshly squeezed) — 1 glass (200 mL)     |  |  |  |  |  |  |  |
| 86. Alcohol-free beer — 1 can/bottle (330 mL)                         |  |  |  |  |  |  |  |
| 87. Beer — 1 can/bottle (330 mL)                                      |  |  |  |  |  |  |  |
| 88. Red wine (young) — 100 mL glass                                   |  |  |  |  |  |  |  |
| 89. Red wine (aged/reserve) — 50 mL glass                             |  |  |  |  |  |  |  |
| 90. White or rosé wine — 100 mL glass                                 |  |  |  |  |  |  |  |
| 91. Cava or sparkling wine — 100 mL glass                             |  |  |  |  |  |  |  |
| 92. Liquor (e.g., whiskey, gin, rum) — 30 mL shot                     |  |  |  |  |  |  |  |

|  |  |  |  |  |  |  |  |
|--|--|--|--|--|--|--|--|
| 93. Sweet liqueurs (Baileys, anise, vermouth)
— 30 mL shot      |  |  |  |  |  |  |  |
| 94. Mixed alcoholic drinks (cocktails, gin & tonic) — 1 glass      |  |  |  |  |  |  |  |
| Section IX: Sweets, Pastries & Snacks (Items 95–113)    |  |  |  |  |  |  |  |
| 95. Pastries (croissants, doughnuts, etc.) — 1 unit                |  |  |  |  |  |  |  |
| 96. Cookies or biscuits — 1 unit or portion (30 g)                 |  |  |  |  |  |  |  |

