| 97. Cakes (sponge cake, pie, etc.) — 1 slice                       |  |  |  |  |  |  |  |
| 98. Chocolate (milk or dark) — 1 portion (30 g)                    |  |  |  |  |  |  |  |
| 99. Chocolates with filling or nuts — 1 portion (30 g)             |  |  |  |  |  |  |  |
| 100. Candies, gummies or sweets — 1 portion (30 g)                 |  |  |  |  |  |  |  |
| 101. Honey or jam — 1 tablespoon                                   |  |  |  |  |  |  |  |
| 102. Ice cream — 1 scoop or small cup                              |  |  |  |  |  |  |  |
| 103. Puddings or custards — 1 portion                              |  |  |  |  |  |  |  |
| 104. Snack bars or energy bars — 1 unit                            |  |  |  |  |  |  |  |
| 105. Potato chips — 1 small bag (30 g)                             |  |  |  |  |  |  |  |
| 106. Salted nuts — 1 handful (30 g)                                |  |  |  |  |  |  |  |
| 107. Popcorn (ready-to-eat) — 1 portion (30 g)                     |  |  |  |  |  |  |  |
| 108. Crackers or breadsticks — 1 portion (30 g)                    |  |  |  |  |  |  |  |
| 109. Savory snacks (nachos, cheese balls, etc.) — 1 portion (30 g) |  |  |  |  |  |  |  |
| 110. Sugar cubes or teaspoons added to drinks — 1 unit             |  |  |  |  |  |  |  |
| 111. Artificial sweeteners — 1 packet or dose                      |  |  |  |  |  |  |  |
| 112. Desserts made at home (custards, rice pudding) — 1 portion    |  |  |  |  |  |  |  |
| 113. Diet or sugar-free sweets — 1 portion                         |  |  |  |  |  |  |  |
| Section X: Miscellaneous (Items 114–137)                    |  |  |  |  |  |  |  |
| 114. Pizza (homemade or commercial) — 1 slice or small unit        |  |  |  |  |  |  |  |
| 115. Lasagna or cannelloni — 1 portion                             |  |  |  |  |  |  |  |
| 116. Stuffed pasta (ravioli, tortellini) — 1 portion               |  |  |  |  |  |  |  |
| 117. Prepared foods (frozen meals, ready dishes) — 1 portion       |  |  |  |  |  |  |  |
| 118. Fried rice or noodles — 1 portion                             |  |  |  |  |  |  |  |
| 119. Couscous or bulgur — 1 portion                                |  |  |  |  |  |  |  |
| 120. Vegetable soup — 1 bowl                                       |  |  |  |  |  |  |  |
| 121. Meat or chicken broth — 1 bowl                                |  |  |  |  |  |  |  |
| 122. Fish soup — 1 bowl  |  |  |  |  |  |  |  |

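### As attached, the FFQ asks only about salted nuts and lists bottled juice and fish soup twice, so aMED and intake changes can be misstated if the form in use matches it

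*Protocol*

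**What the plan says.** Section 5.7.1 of the protocol describes a 137-item FFQ, validated in the Spanish population. The reported frequency of each food is "multiplied by the weight of the portion sizes indicated in the questionnaire", and nutrient intake is then adjusted for energy. The same section defines aMED on a 0 to 9 scale, "which includes the intake of vegetables, legumes, fruits, nuts, grains, red and processed meats, fish", plus a fat ratio and alcohol: nine components in all. Table 2 schedules the FFQ and MEDAS at all three visits but has no row for aMED or aHEI, so both appear to be computed from the FFQ. Section 6.4 sizes the study at 26 family units for a 1-point paired difference in aMED.

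Section 14 attaches an English version of the FFQ, labelled as a translation of the Spanish form. Its only line for nuts eaten as such is "106. Salted nuts — 1 handful (30 g", placed among sweets and snacks. The one other line that mentions nuts is a confectionery item, "99. Chocolates with filling or nuts — 1 portion (30 g". Bottled juice appears as "5. Bottled or canned fruit juice (200 mL" and again as "85. Bottled fruit juice (not freshly squeezed) — 1 glass (200 mL". Fish soup appears at items 66 and 122. Potato chips appear in "26. French fries or potato chips (1 portion" and again in "105. Potato chips — 1 small bag (30 g". The attached form carries no instruction to report a food on one line only, and section 5.7.1 gives no rule for overlapping lines.

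**The concern.** The study asks whether nutrition education given for the child changes what the parents eat. A parent who starts eating unsalted almonds or walnuts has nowhere to record it. A parent who replaces salted nuts with plain ones records a fall in nuts when intake has not fallen. No later scoring rule can recover intake that was never asked about.

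The repeated lines raise a different problem. If a parent reports the same juice or soup on both lines and the lines are summed, that food counts twice. A constant intake cancels in a paired comparison, but a change does not: it is recorded at up to twice its size, and it also feeds the energy total used for adjustment. Fish soup bears on the fish component of aMED, couscous on grains, and juice on fruit if juice is scored there. aMED is the index that sizes the study, so errors in its inputs matter more than errors in an incidental food group.

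**Working it through.** **1. The plan's own figure.** Inputs from section 6.4: 26 units, a difference of 1 aMED point, a paired comparison, 80% power and 5% alpha (two-sided assumed; sidedness is not stated). The SD is not given, so 26 cannot be reproduced, only solved backwards. From n = (SD × (1.960 + 0.842) / difference)², SD = √26 / 2.802 = 5.099 / 2.802 = 1.82. The exact paired t-test gives 1.75, which is used below.

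**2. Nut lines.** Across the 137 items, nuts occur in item 106 (salted only) and item 99 (filled or nut chocolates). Item 9, dried fruit, names only fruits. So one of the nine aMED components rests on a line restricted to salted nuts.

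**3. Repeated lines.**
- True repeats: bottled juice (5 and 85, both 200 mL) and fish soup (66 and 122).
- Partial overlaps: chips (26 also covers fries; 105 is chips alone); couscous (31 and 32 also cover rice and pasta; 119 also covers bulgur); rice pudding (37 also covers yogurt; 112 also covers home-made custards); custards (103 and 112); eggs (55 in general, 56 to 58 by preparation).
- Bearing on aMED: fish soup, couscous and possibly juice directly. Chips, eggs and desserts act mainly through energy and nutrients, and on aMED at most through the fat ratio.

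**4. Double counting, juice example.** A fall from one glass a day to one a week is 200 − 200/7 = 171 mL/day. If both lines are answered in full and summed, the record shows 2 × 171.4 = 343 mL/day. If a share s of parents does this, the mean change is recorded as 171.4 × (1 + s). The share is unknown; as assumed values:
- s = 25%: 214 mL/day
- s = 50%: 257 mL/day
- s = 100%: 343 mL/day

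A parent who stays at one glass a day is recorded at 400 mL at each visit, so the change is 400 − 400 = 0, as it should be. For fish soup, the form gives a portion and a bowl without weights, so no figure can be computed.

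**5. Missed nut points, illustration only.** The nut component moves one parent's aMED by at most 1 point. If a share p of parents truly gains that point and the form misses it, the mean change is understated by p × 1. Take a true mean change of 1 point, 26 parents (one per family) and an SD of differences of 1.75:

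| Share missed | Parents of 26 | Recorded mean change | Power | N for 80% power |
|---|---|---|---|---|
| 0 | 0 | 1.00 | 80.0% | 26 |
| 5% | 1.3 | 0.95 | 75.9% | 29 |
| 1/9 | 2.9 | 0.89 | 70.2% | 33 |
| 20% | 5.2 | 0.80 | 61.1% | 40 |

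The shares are assumptions. The protocol gives no aMED cut-offs, so whether any given parent would gain or lose the point cannot be worked out.

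**The case against.** The strongest reply is that the attached form may not be the form that families complete. It is labelled a translation, the hospitals are in Catalonia, and section 5.7.1 names a questionnaire validated in Spain. If the Spanish form asks about nuts in general and has no repeats, the fault lies in the appendix and no data are affected. This stands, and it is why the conclusion is conditional. The appendix still needs correcting in that case, because the protocol presents it as its instrument.

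A second reply is that scoring overlapping lines is commonly left to the SAP or a scoring manual. That is fair for the absence of a summing rule. It does not answer the nut line, where the information is never collected, nor the lack of a respondent instruction, without which nobody can tell afterwards whether the same glass was reported twice.

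A third reply is that several overlaps are only partial, and that MEDAS, collected separately at every visit, does not depend on these lines. Both are right. Counting each overlapping pair once would discard real intake of fries, rice, pasta, yogurt or eggs. MEDAS gives an independent reading of Mediterranean diet adherence, but it is not the index used to size the study.

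A reader might infer that the nut line alone could create or erase the 1-point difference the study is designed to detect. The documents do not support that. One point is the maximum for an individual, whereas the design difference is a mean; a 1-point shift in the mean would need every parent misclassified in the same direction.

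**Conclusion.** The point holds in conditional form. Used as attached, the FFQ cannot record unsalted nuts, would read a switch from salted to plain nuts as a fall, and can double-count bottled juice and fish soup. Changes in these foods, in energy and in some aMED components can therefore be misstated.

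A reader might go further and conclude that the trial's aMED changes are misstated. That would require knowing that the administered Spanish form has the same lines, that parents answer both repeated lines for the same intake, and that the lines are summed; the protocol establishes none of these. The size and direction of any aMED bias cannot be derived. The power figures of 76% to 61% rest on assumed shares and a back-solved SD, and show only that a few missed nut points among 26 parents are enough to matter. The check is cheap and protects the index behind the sample size, so it should be made.

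**What to change.** 1. Compare the appendix line by line with the validated Spanish form actually administered. If only the translation is at fault, correct the appendix and stop there.
2. If the form in use has only the salted-nut line, give newly enrolled families a line covering all nuts. Keep the same wording at all three visits within each family: changing it between a parent's baseline and 12-month visit would produce a spurious rise. Report aMED with and without the nut component.
3. If the repeats are in the form in use, score 5/85 and 66/122 once, for example by taking the larger of the two answers, and state this in section 5.7.1.
4. For the partial overlaps (26/105, 31/32/119, 37/112, 103/112 and 55 to 58), instruct newly enrolled respondents to report each food on one line only. Do not drop a whole line. For data already collected, run a sensitivity analysis on how these lines are combined.

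The cost is a document check, one reworded line, a short instruction and a few lines of scoring code. The drawback is that the nut item would differ between earlier and later families, though not within any family's paired change. The report with and without nuts shows how much the results depend on that component.
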